## COVER PAGE

Study Title	Interventions To Help Asthma Clinical Adherence (ITHACA)
NCT Number	NCT02999789
Document Description	Statistical Analysis Plan
Document Date	23 February 2021

This study was a quasi-experimental single-center pilot trial that used a staggered implementation design which measured the effect of an asthma medication reminder system device on asthma controller medication adherence during an initial run-in period and an intervention period. Because the intervention was a reminder system, it was not possible to 'blind' the participants.

For the pilot phase, we aimed to recruit children ages 5 to 17 years with a diagnosis of persistent asthma who required a daily inhaled corticosteroid metered dose inhaler and whose guardian was the person responsible for directly administering or supervising the administration of their daily asthma medication. Our target sample size at the study's onset was to recruit 30 children ages 5 to 17. The sample size was limited by the budget limitations. Based on cost-efficiency and limitations, 30 participants would give a general estimate of the effectiveness of this intervention. The study results could be used for the power calculations for a future, larger RCT. Assuming a positive effect of reminder systems and a baseline adherence rate of 60%, with 15 patients in each group, with a power of 0.80, an alpha of 0.05, there would be enough power to detect a 15% change in adherence which is within the range of improvement reported. This percentage change translated to a Number Needed to Treat (NNT) of 6 patients.

We only recruited from a University-affiliated clinic serving publicly insured children. We recruited children whose asthma subspecialist or health care provider practiced at the Children's Health Center (CHC) at Zuckerberg San Francisco General Hospital. We only recruited from the primary care clinics and the asthma clinic. We only recruited children whose guardian responsible for administering their daily asthma medication had Limited English Proficiency (LEP) and whose primary language was Spanish. Lastly, we only included children whose daily inhaled corticosteroid was a metered dose inhaler (MDI) that was either Flovent (fluticasone propionate) HFA (Hydrofluoroalkane) or Qvar (beclomethasone dipropionate) HFA. This was the case because the SmartInhaler device was only available for those two MDIs.

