## DATA ANALYSIS

In order to analyze the data, we consulted a statistician from the UCSF Clinical and Translational Science Institute (CTSI). The statistician analyzed the entire data set using statistical software. Demographic characteristics of each group were assessed to see if there were obvious disproportionate distributions of certain characteristics in the groups which may have affected the adherence. Medication adherence for each medication was calculated as a percentage of the total number of doses received during the study period divided by the total number of doses prescribed. As a result, this percentage ranged from 0 to 100. Medication adherence percentages and asthma symptom control scores during both the run-in and intervention periods were measured and the differences between the two time periods (Adherence Delta  $\Delta$  and asthma symptom control Delta) was calculated for each patient. For objectives 1 & 2, we compared the mean “adherence delta” and “asthma symptom control delta” for each group using a student t-test.

Finally for the third objective, in order to assess if there were specific patient behavior characteristics which were associated with the success of a novel asthma medication reminder system, we identified those patients whose adherence rates increased from baseline. We compared the scores of the RAM Scale for those patients with a change in adherence compared to those patients with no improvement in adherence. We used a chi-squared test to assess if the RAM scores which suggest 'forgetful nonadherence' were associated with improved adherence rates during exposure to the reminder system. Analyses were performed using SAS version 9.4 (SAS Institute, Cary, NC).

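### Objective 3 reduces each child's measured adherence change to improved or not and tests it by chi-squared in about 30 children, giving up a quarter or more of the power that the continuous change would have

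*SAP*

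**What the plan says.** All of the relevant method is in the SAP, Data Analysis. Adherence is a percentage from 0 to 100 in the run-in and intervention periods, and the difference between the two periods, the adherence delta, "was calculated for each patient". For objectives 1 and 2 the mean deltas are compared "for each group using a student t-test".

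For objective 3 the same variable is handled differently. The SAP states that "we identified those patients whose adherence rates increased from baseline", and then that RAM scores were compared "for those patients with a change in adherence compared to those patients with no improvement in adherence". No test is named for that comparison of scores. The only named test is in the next sentence, which begins "We used a chi-squared test to assess if the RAM scores which suggest" and goes on to relate forgetful nonadherence to improved adherence under the reminder. No minimum gain is set, so any rise counts as improvement.

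On size, the sample-size paragraph under Cover Page says "Our target sample size at the study's onset was to recruit 30 children ages 5 to 17". It claims power for a 15% change in adherence but none for objective 3.

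**The concern.** The delta is treated as continuous in one paragraph and as a sign in the next, without a reason. A child who gains 1 point and a child who gains 40 count alike. With about 30 children there is little information to spare, and the cut at zero becomes less efficient the better the reminder works, because fewer children remain on the not-improved side.

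Two things are at stake. A real difference between RAM types is more likely to be missed than it need be. And the cover page offers the results as input to power calculations for a larger trial, whereas a sign-only chi-squared yields neither a difference in percentage points by RAM type nor an interval for it.

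**Working it through.** **The plan's own figure.** The SAP states no power for objective 3, so there is nothing to reproduce directly. Its one power statement (15 per group, power 0.80, alpha 0.05, 15% change) is used here only to find a plausible SD. Read as a difference in means, a two-sided t-test with 15 per group has 80% power at a standardised difference of 1.06, so the implied SD is 15/1.06 = 14.2 points. The SAP does not state this SD, so a range of 14, 20 and 25 is used.

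**Inputs.**
- From the SAP: 30 children; alpha 0.05; 15-point change.
- Assumed: two-sided test; normal deltas with equal SD in the two RAM types; overall mean gain of 15 points; true difference between forgetful-type and other children of 1 SD; nF forgetful and nO other children as 15/15, 20/10 or 10/20.

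**t-test on the delta.** Noncentral t on 28 df with noncentrality 1 × √(nF·nO/30). For 15/15 this is √(225/30) = 2.739, power 75%. For 20/10 or 10/20 it is √(200/30) = 2.582, power 70%.

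**Chi-squared on the sign.** In SD units the forgetful mean is 15/SD + nO/30 and the other mean is 15/SD − nF/30. The probability of improving is Φ of each. Example, 15/15 and SD 14: 15/14 = 1.071, giving Φ(1.571) = 94% and Φ(0.571) = 72%. Power is the total probability of all 2x2 tables whose uncorrected Pearson statistic is at least 3.841. The smallest expected cell is min(nF, nO) × (1 − overall proportion improved); in the example 15 × (1 − 0.829) = 2.6.

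| Forgetful/other | SD | Improved: forgetful, other | Smallest expected cell | t-test | Chi-squared | Relative loss |
|---|---|---|---|---|---|---|
| 15/15 | 14 | 94%, 72% | 2.6 | 75% | 37% | 51% |
| 15/15 | 20 | 89%, 60% | 3.8 | 75% | 49% | 34% |
| 15/15 | 25 | 86%, 54% | 4.5 | 75% | 53% | 30% |
| 20/10 | 14 | 92%, 66% | 1.7 | 70% | 43% | 40% |
| 20/10 | 20 | 86%, 53% | 2.5 | 70% | 50% | 29% |
| 20/10 | 25 | 83%, 47% | 2.9 | 70% | 53% | 25% |
| 10/20 | 14 | 96%, 77% | 1.7 | 70% | 11% | 85% |
| 10/20 | 20 | 92%, 66% | 2.5 | 70% | 28% | 60% |
| 10/20 | 25 | 90%, 61% | 3.0 | 70% | 35% | 50% |

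Relative loss is 1 − chi-squared power / t-test power, from unrounded values. Five of the nine cells lose clearly less than half; four lose half or more.

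**Second check, 15/15, t-test power fixed at 80%** (difference 1.06 SD). Chi-squared power is 0.605, 0.59, 0.54, 0.44 and 0.17 when the mean delta is 0, 0.5, 0.75, 1.0 and 1.5 SD above zero. Even with the cut in the middle of the deltas the loss is 1 − 0.605/0.80 = 24%.

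**Bounded scale.** Deltas of percentages are not exactly normal. A simulation with adherence kept within 0-100 (run-in mean 60, delta SD about 14.5, 15-point difference) gave t-test, Wilcoxon and chi-squared power of 60%, 56% and 35% at 15/15, and 53%, 48% and 14% with 10 forgetful and 20 other. The ordering is the same.

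**Type I error.** At 15/15 the exact size of the uncorrected chi-squared is 0.046, 0.055, 0.041 and 0.012 when 50%, 70%, 85% and 93% of children improve. The cost is power, not false positives.

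**The case against.** The strongest reply is that objective 3 can be read as a responder question: which behaviour types go with success of the reminder. A 2x2 table answers that naturally, if inefficiently. The study is also a budget-limited pilot that claims no power for this objective, and the 1-SD effect, the SDs and the RAM splits above are not in the SAP. Finally, the SAP is written in the past tense, so replacing the stated test now could be a post-hoc switch. All of this stands as a limit on wording, rating and remedy. None of it restores the discarded information: chi-squared had less power in every scenario run, and a pilot has most use for an estimate.

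A reader might infer more than the documents support:
- **That the test halves the power in general.** It does not. The loss runs from 25% to 85% over the grid, and the SAP fixes neither SD nor split. The 10/20 figures apply only when forgetful children are the minority; with 20 forgetful and 10 other the loss is 25-40%.
- **That the table carries almost no contrast if the reminder works.** At 15/15 and SD 14, improvement is still 94% against 72%.
- **That the two groups overlap, since a child whose adherence fell has both changed and not improved.** The phrase "for those patients with a change in adherence compared to those patients with no improvement in adherence" is loose, but the sentences on either side make clear that an increase is meant.
- **That a null result would be reported as RAM type not mattering.** The SAP says nothing of the kind.

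**Conclusion.** The point holds as an avoidable loss of information. Under the stated assumptions, power falls from 70-75% to 37-53% at an even split, to 43-53% with 20 forgetful and 10 other children, and to 11-35% with 10 and 20. That is about a quarter to a third in many scenarios. It is about half at an even split when some 83% of children improve, and half or more when forgetful children are the minority. Smallest expected cells of about 1.7 to 4.5 show how thin the table would be, although this does not inflate type I error.

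Confidence is high that information is lost. The size of the loss is conditional on an SD and a RAM split that the SAP does not give. Severity is minor: this is the third objective of a pilot, and the other objectives are unaffected.

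**What to change.** Make the main objective 3 analysis a comparison of the continuous adherence delta between forgetful-type and other children by t-test, as already used for objectives 1 and 2, with a Wilcoxon rank-sum test as a check. Report the difference in percentage points with a 95% CI. Use the same RAM classification that the chi-squared test would have used. Keep the 2x2 table as description, with the groups worded as improved and not improved.

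The cost is about two sentences of SAP text and one further run on deltas already calculated. There are two small downsides. The answer becomes a mean difference rather than a responder proportion, which the retained table still shows. And if the data have already been analysed by chi-squared, that result should still be reported and the continuous comparison labelled as added afterwards.
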